11.2. Data-Analysis

Unless otherwise specified, all BOLD, genetic, behavioral, self-report and physiological data will be analyzed with AFNI or R (http://www.R-project.org; R Development Core Team, 2008). The types of statistical analysis to be utilized in the current protocol are summarized below.

Nicotine deprived vs non-deprived. Between condition (nicotine-deprived vs non-deprived) comparisons will be conducted on self-report, behavioral, BOLD ROI, resting CBF and ERP responses with a series of one-way repeated measures ANCOVAs, with nicotine-deprivation (nicotine-deprived vs non-deprived) as the within-subjects factor and nicotine dose as the covariate. By controlling for nicotine dose we can partially dissociate the

Principal Investigator: [name].

effects from acute nicotine-withdrawal effects. Treatment seeking status (Treatment seeking vs non-treatment seeking) will be included as a between-subjects factor in these models to assess the main effects and of motivation to quit as well as any interaction between motivation to quit and acute nicotine withdrawal.

Date: March 2, 2022

Mediation. Where mediation has been hypothesized (e.g., central CRF as a mediator of VS reactivity following acute nicotine withdrawal), regression coefficients for the paths of each mediation model will be derived with multiple regression and the mediation effect will be tested with ProdClin (Mackinnon, Fritz, Williams & Lockwood, 2007). ProdClin is a program developed by MacKinnon, Fritz, Williams, and Lockwood (2007) that uses the distribution of the product of paths a and b to compute asymmetric confidence intervals for the mediated effect. ProdClin is an alternative to the Sobel (1982) method that provides a more powerful and accurate test of the mediation effect because it is based on an asymmetric distribution which more closely resembles the true distribution of the product terms. Mediation models will be conducted separately for treatment-seeking and non-treatment seeking smokers.

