Functional Connectivity. Seed regions for FC will be based on peak BOLD responses in ROIs for the parameter of interest. Strength of functional connectivity will be measured by correlating the BOLD time-series between seed and target regions. Fisher r to z transformations will be conducted to test for significant differences in functional connectivity strength between the non-deprived and nicotine-deprived conditions. Treatment seeking status (Treatment seeking vs non-treatment seeking) will be included as a between-subjects factor in these models to assess the main effects and of motivation to quit as well as any interaction between motivation to quit and acute nicotine withdrawal.

Correlational analyses. Bivariate partial correlations controlling for nicotine dose will also be conducted between self-report and behavioral indices of acute nicotine withdrawal and BOLD indices. Correlational analyses will serve to identify neural markers of responsivity to nicotine replacement. A series of bivariate partial correlations (controlling for nicotine dose) will also be conducted between BOLD, EEG, psychophysiological and neuroendocrine markers between nicotine-deprived and non-deprived conditions. Correlations will be conducted separately for non-treatment and treatment seeking groups.

Genotype by nicotine-deprivation interaction. 2 x 2 mixed-design ANOVAs will be conducted with genotype (short vs long allele of the 5-HTTLPR gene) varied between-subjects, and nicotine-deprivation (nicotine deprived vs non-deprived) varied within-subjects. The DVs will be BOLD signal change and functional connectivity. Treatment seeking status (Treatment seeking vs non-treatment seeking) will be included as a between-subjects factor in these models to assess the main effects and of motivation to quit as well as any interaction between motivation to quit and acute nicotine withdrawal.

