RSN dynamics under acute nicotine withdrawal. The presence of three independent RSNs resembling the ECN, DMN and SN will be confirmed by applying an Independent Component Analysis (ICA) to the band pass filtered (0.01 to 0.08 Hz) resting BOLD time-series. ICA analysis will be conducted using the FSL Melodic ICA software (http://www.fmrib.ox.ac.uk/analysis/research/melodic/). The time-series of six seed regions reflecting core-nodes within each of these networks (ECN: dlPFC, PPC; DMN: vmPFC, PCC; SN: dACC, anterior insula) will then be regressed against each other to assess within and between network rsFC. Fisher r to z transformations will be applied to assess changes in rsFC between nicotine-deprived and non-deprived conditions. Bivariate partial correlations (controlling for nicotine dose) will also be conducted between the degree of change in rsFC within/between the three networks and changes in self-reported affective/cognitive withdrawal symptoms/urge to smoke as well as changes in working memory and attention indices. Treatment seeking status (Treatment seeking vs non-treatment seeking) will be included as a between-subjects factor in these models to assess the main effects and of motivation to quit as well as any interaction between motivation to quit and acute nicotine withdrawal. Correlations will be conducted separately for non-treatment and treatment seeking groups.

Principal Investigator: [name].

Relapse vs non-relapse group comparisons. Neurobiological processes underlying acute nicotine withdrawal will be assessed as a function of relapse status at each of the follow-up time-points by conducting between group comparisons.

Date: March 2, 2022

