Correlational. Bivariate partial correlations (controlling for nicotine dose) will be conducted between the change in BOLD, ERP/EEG, psychophysiological and neuroendocrine markers, behavioral and self-report under nicotine-deprivation (relative to nicotine satiety). Large effects (d > 0.80) are typically observed between changes in self-report (e.g., craving, withdrawal symptoms) and BOLD measures (e.g., insula or amygdala activity or functional connectivity) during smoking abstinence relative to smoke adlib (Cole et al., 2010; Kozink et al., 2010a; McClernon et al., 2009b). Similarly large effect sizes are reported between changes in behavioral indices (e.g., RT variability) and BOLD responses (e.g., PCC task response) under nicotine (relative to placebo) in minimally deprived smokers (Hahn et al., 2007). Large effect sizes also arise between BOLD responses and neuroendocrine and psychophysiological markers (Ahs, Sollers, Furmark, Fredrikson, & Thayer, 2009; Drevets et al., 2002) as well as between behavioral indices and time-to-smoke in the laboratory relapse model (Dallery & Raiff, 2007). Based on a slope of 0.59 between each predictor and outcome measure (a large effect size according to J. Cohen, 1988) a sample size of at least 20 would be required to achieve a power of 0.80. (Calculated by G*Power, http://www.psycho.uniduesseldorf.de/abteilungen/aap/gpower3/).

Mediation Analyses. Based on the literature reviewed above, we expect a large effect size between each predictor, outcome and mediation variable in the mediation models described above. Based on a large effect size for paths *a* and *b*, Fritz and McKinnon (2007) suggest a sample of 35 to achieve a 0.80 power to detect each mediation effect with Prodclin.

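### Main Study change-score correlations and mediation paths leave out scan order, which counterbalancing does not protect; the tDCS section gives no session-position term and no three-condition model

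*Combined protocol and SAP*

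**What the plan says.** **Main Study correlations.** Section 11.2 (Correlational analyses) plans the following: "Bivariate partial correlations controlling for nicotine dose will also be conducted between self-report and behavioral indices of acute nicotine withdrawal and BOLD indices". Their purpose is stated: "Correlational analyses will serve to identify neural markers of responsivity to nicotine replacement". They are split by group: "Correlations will be conducted separately for non-treatment and treatment seeking groups". That paragraph speaks of indices; two other places show that changes are meant. Section 11.2 (RSN dynamics) has "Bivariate partial correlations (controlling for nicotine dose) will also be conducted between the degree of change in rsFC within/between the three networks", set against changes in symptoms and urge to smoke. Section 11.4 (Correlational) has "Bivariate partial correlations (controlling for nicotine dose) will be conducted between the change in BOLD, ERP/EEG, psychophysiological and neuroendocrine markers, behavioral and self-report", measured under deprivation relative to satiety.

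**Mediation.** Section 11.2 says that "regression coefficients for the paths of each mediation model will be derived with multiple regression and the mediation effect will be tested with ProdClin", and "Mediation models will be conducted separately for treatment-seeking and non-treatment seeking smokers". No covariates are listed.

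**Mean contrast.** The repeated-measures ANCOVAs are specified "with nicotine-deprivation (nicotine-deprived vs non-deprived) as the within-subjects factor and nicotine dose as the covariate", with treatment-seeking status added between subjects.

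**Order.** Sections 4.1 and 4.4(iii) counterbalance the deprived and non-deprived scans across participants. No model in Section 11 contains an order, session or period term.

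**tDCS arm.** Section 24.6 randomises the order of the three stimulation conditions within a visit day, and of the patch across smokers' two days. Section 24.12 refers back to Section 11 and adds only power text. That text names a two-tailed paired t-test, described for anodal stimulation against sham. The first primary outcome in the Précis names tDCS condition as a contrast. No session-position term is given, and there is no model for three conditions.

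**The concern.** Counterbalancing makes session effects cancel in a mean difference. They do not cancel in a correlation between two differences. If a measure drifts from scan 1 to scan 2, the drift adds to the deprived-minus-satiated change in people deprived second and subtracts from it in people deprived first. Two measures that drift in the same direction then rise and fall together across the two order groups, with no link between them within a person. Drifts in opposite directions offset a real link.

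The correlations are the route to neural markers of response to nicotine replacement, and the mediation models test the central mechanisms. Hypothesis 2.1, for example, makes plasma ACTH a mediator of negative affect and of amygdala and BNST reactivity. A shared drift is plausible for the shock task. Section 4.4 withholds shock until the first scan visit because it expects repeat exposure to blunt the response. BOLD, self-report and ACTH are all collected in that same afternoon session.

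**Working it through.** **Plan's own figures.** Section 11.4 asks for at least 20 people at a slope of 0.59, power 0.80, alpha 0.05. By Fisher z, two-sided: N = ((1.960 + 0.842)/atanh(0.59))² + 3 = (2.802/0.678)² + 3 = 20.1. Section 24.12 asks for about 34 per group; a two-sided paired t-test at d = 0.5 has power 0.81 at n = 34. Both reproduce, and neither is in dispute.

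**Inputs.** Group sizes are 85 and 35 planned completers (Section 11.5) and alpha is 0.05 (Section 11.3), taken as two-sided because that reproduces the 20. Order is coded s = +1 if deprived at scan 2 and -1 if deprived at scan 1, about half each. The shift π is the average scan 2 minus scan 1 effect, in SDs of the change score within order. All values of π are assumptions.

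**Model.** Change score D = τ + sπ + e. With balanced order the mean of s is 0, so the mean of D is still τ. For two measures with true correlation ρ:

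r = (ρ + π₁π₂) / √[(1 + π₁²)(1 + π₂²)]

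**Creating an association (ρ = 0, equal shifts).** Simulated false-positive rates of the partial correlation:

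| π in both | induced r | n = 85 / 35, dose only | dose and order |
|---|---|---|---|
| 0.2 | 0.04 | 6% / 6% | 5% |
| 0.3 | 0.08 | 11-12% / 7-8% | 5% |
| 0.5 | 0.20 | 46% / 21% | 5% |

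Hand check for 0.5 at n = 85 with one covariate: atanh(0.20) × √(85 - 1 - 3) = 0.203 × 9 = 1.82, and P(Z > 1.96 - 1.82) is about 0.45. Unequal shifts of 0.5 and 0.2 give 13% / 8%. A shift in one measure only gives 5% / 5%.

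**Scale.** Section 11.4 assumes a correlation of 0.5 between repeated measures, so the SD of the change is √(2(1 - 0.5)) = 1 raw SD. A 0.5 SD shift therefore equals the planned drug effect, d = 0.5.

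**Hiding an association (planned ρ = 0.59, opposite shifts).** At 0.3 SD, r = (0.59 - 0.09)/1.09 = 0.46. Power at n = 85 / 35 is 0.99 / 0.80 without order, against above 0.99 / 0.96 with it. At 0.5 SD, r = 0.27 and power is 0.72 / 0.31 without order.

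**Mediation.** The plan does not say how the paths are formed. Assume change-score regression, a mean mediator change of 0.8 SD and no true path from mediator to outcome. The product interval then errs in 13% / 9% (0.3 SD in both) and about 49% / 23% (0.5 SD), against 5-6% with order. The first path, a mean within-person change, is protected by counterbalancing; the second is not.

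**Mean contrast.** Pooled n = 85 + 35 = 120, d = 0.5, shift 0.5 SD: the standardised effect is 0.5/√1.25 = 0.45, and power exceeds 0.99 with or without order.

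**What order leaves behind.** Assume individual shifts with mean 0.5 SD, SD 0.5 and correlation 0.5 between the two measures. After order adjustment the residual r is 0.125/1.25 = 0.10. The false-positive rate is 14% / 8-9% with order, against 64% / 31% without.

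**tDCS.** The squared gaps in position between two of three sessions are 1, 1 and 4, mean 2. A linear trend of t SD per session multiplies the variance of the anodal-sham difference by 1 + 2t², that is 1.08, 1.18 and 1.50 for t = 0.2, 0.3 and 0.5. Power at n = 34 falls from 0.81 to 0.78, 0.74 and 0.64.

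**The case against.** The case against has real force on size. The documents give no session effect. The shock passage supports a direction for one task and says nothing about resting connectivity, go/no-go performance or withdrawal scores. Mock-scanner training, refreshers, practice before each scan and individually set go/no-go difficulty should all limit practice effects. At 0.2-0.3 SD the error rate is 6-12%; the alarming figures need a nuisance shift as large as the drug effect, in both measures. At the planned correlation of 0.59, opposite 0.3 SD shifts do little harm at n = 85. All of this stands, and it makes the harm conditional. None of it supplies the missing term.

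Three stronger readings should be resisted:

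- A reader might infer that the deprivation contrast itself is biased. Counterbalancing protects it.
- A reader might infer that the tDCS analysis names no condition comparison at all. Section 24.12 names the paired anodal versus sham test, and the Précis names tDCS condition in the first primary outcome.
- A reader might infer that one covariate removes the problem entirely. It removes the average shift only; correlated individual differences in habituation or practice remain.

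On tDCS, randomised order means that omitting position costs power only. Even that loss depends on an assumed trend, and the planning effect size, drawn from a meta-analysis, may already contain that variance.

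**Conclusion.** The point holds for the Main Study correlations and for the mediator-to-outcome paths. As written, they adjust for dose at most, and counterbalancing does not protect them. The size is unknown: negligible if the average shift is 0.2 SD or affects one measure only, modest at 0.3 SD, and serious at 0.5 SD, above all in the larger group. The figures rest on assumed shifts and, for mediation, on an assumed change-score form. The documents do not show that any particular marker would be false.

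The tDCS part is secondary and a matter of specification. The reversed-polarity condition has hypotheses in Section 24.3 but no stated test. The predicted ordering of abstinent smokers, sated smokers and controls has no model. Position within the day is not addressed.

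The change is recommended because it is cheap and uses a variable that the trial already assigns. No result is shown to be invalid without it.

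**What to change.** **Section 11.2.** Add order (which condition came first) as a covariate beside nicotine dose in every change-score correlation and every mediation path. Order in the deprivation ANCOVAs is optional. State that the adjustment removes the average session shift only.

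The cost is wording and one degree of freedom. With no session effect, power for r = 0.59 goes from 0.80 to 0.77 at n = 20 and is essentially unchanged at 35 and 85. For r = 0.3 at n = 85 it goes from 0.81 to 0.80.

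**Section 24.12.** If a mixed model is stated, use participant as a random effect. The fixed effects should be tDCS condition, session position, smoker group, patch and visit day (smokers only), and the condition-by-patch and condition-by-group interactions that the hypotheses need. Define position for sessions that are repeated or split across days, which Section 24.6 allows.

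With the six orders balanced, position costs no precision. Under simple randomisation of 34 people (an assumption, since the figure showing the method is not available) the variance rises by about 3% on average. A preceding-condition term raises the variance of the anodal-sham contrast by 25% (0.333 to 0.417), so keep it for a sensitivity analysis.

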Aim 2: To examine the effect of acute nicotine withdrawal on self-reported negative affect (anxiety, irritability) and stress reactivity, and in turn on reactivity in the amygdala and BNST. Acute nicotine withdrawal produces marked elevations in negative affect and enhanced stress reactivity. Although preclinical literature is limited, there is some evidence that these effects may be mediated by enhanced central CRF acting at the amygdala and BNST. Neuroimaging studies have linked individual differences in negative affect and stress reactivity to amygdala reactivity as well as top down regulation from the rostral ACC. Both amygdala reactivity and rACC-amygdala connectivity are in turn mediated by the short/long allele polymorphism in the 5-HTTLPR gene.

Measures: Self-reported negative affect (e.g., anxiety, irritability) and craving; BOLD response and functional connectivity during amygdala reactivity task and USCRT.

Mediators: Plasma ACTH; 5-HTTLPR short/long allelic polymorphism

Hypothesis 2.1: Compared with nicotine satiety, acute nicotine withdrawal will result in enhanced negative affect (e.g., anxiety, irritability), accompanied by enhanced amygdala and BNST reactivity. These effects will be partially mediated by an increase in plasma ACTH (as a marker of central CRF).

Hypothesis 2.2: The effect of nicotine withdrawal on amygdala reactivity will be partially mediated by reduced regulatory input from the rACC. During nicotine withdrawal we expect the rACC (and other DMN regions) to be engaged in rumination on craving and affective symptoms. Consequently, we expect reduced task-related regulatory input from the rACC to the amygdala, manifesting in reduced rACC-amygdala effective connectivity during an amygdala reactivity task.

Hypothesis 2.3: The effect of acute nicotine withdrawal on amygdala reactivity and rACC-amygdala connectivity will be most pronounced among individuals expressing the short allele of the 5-HTTLPR gene.

Hypothesis 2.4: Larger changes in amygdala and BNST reactivity will be associated with poorer treatment outcomes.

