12.1 Subject selection

Participant recruitment will be based strictly on the inclusion/exclusion criteria. No preferences in participant recruitment will be made on the bases of gender, race, or ethnic background. Efforts will be made to avoid participant distribution bias such that if skewing is noted, subjects in the over-represented group may temporarily be excluded from the study until additional participates from under-represented groups can be established.

Efforts will be made to include ethnic minorities in proportion to their presence in the major metropolitan Baltimore area (Baltimore City, Anne Arundel, and Baltimore and Howard counties; http://quickfacts.census.gov/qfd/states/24/24510.html).

Treatment seeking smokers

	APPROVED STUDY POPULATION							
	FEMALE	MALE	TOTAL	FEMALE	MALE	TOTAL		
	ENROLLMENT ENROLLMENT ENROLLMENT COMPLETERS COMPLETER							
APPROVED CEILING	APPROVED 61 50 120 43 42 85							

NIH TARGETED/PLANNED ENROLLMENT					
	Sex/Gender				
ETHNIC CATEGORY	Females	Males	Total		
Hispanic or Latino	3	2		5**	
Not Hispanic or Latino	58	57	115		
Ethnic Category: Total of All Subjects*	61	59		120*	
RACIAL CATEGORIES					
American Indian/Alaska Native	0	0	0		
Asian	2	2	4		
Native Hawaiian or Other Pacific Islander	0	0	0		
Black or African American	39	38	77		
White	20	19	39		
Racial Categories: Total of All Subjects*	61	59		120*	

^{*}The "Ethnic Category: Total of All Subjects" must be equal to the "Racial Categories: total of All Subjects."

Non-treatment seeking smokers

APPROVED STUDY POPULATION								
	FEMALE	MALE	TOTAL	FEMALE	MALE	TOTAL		
	ENROLLMENT ENROLLMENT ENROLLMENT COMPLETERS COMPLETERS COMPLETER							
APPROVED CEILING	APPROVED 21 21 42 18 17 35							

Principal Investigator: [name].

NIH TARGETED/PL/	ANNED ENROLLMEN		
		Sex/Gender	
ETHNIC CATEGORY			
	Females	Males	Total
Hispanic or Latino	1	1	2**
Not Hispanic or Latino	20	20	40
Ethnic Category: Total of All Subjects*			42*
RACIAL CATEGORIES			
American Indian/Alaska Native	0	0	0
Asian	1	0	1
Native Hawaiian or Other Pacific Islander	0	0	0
Black or African American	13	13	26
White	7	8	15

Date: March 2, 2022

21

42*

Older individuals, defined as those over 55, will be excluded from the present study. *Justification:* Many cognitive processes change with age. In addition, the risk of difficult-to-detect medical abnormalities such as silent cerebral infarcts increases with age.

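### The 5-HTTLPR by deprivation model has no race or ancestry term in a sample planned as 64% Black and 33% White, so the interaction behind Hypothesis 2.3 is open to confounding if allele carriage and deprivation response both differ by ancestry

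*Combined protocol and SAP*

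**What the plan says.** Hypothesis 2.3 (Section 2.3) is about effect modification: "The effect of acute nicotine withdrawal on amygdala reactivity and rACC-amygdala connectivity will be most pronounced among individuals expressing the short allele" of 5-HTTLPR. Section 2.2 places the polymorphism among the secondary goals.

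Section 11.2 tests it as follows: "2 x 2 mixed-design ANOVAs will be conducted with genotype (short vs long allele of the 5-HTTLPR gene) varied between-subjects", with deprived versus non-deprived varied within subjects. On outcomes: "The DVs will be BOLD signal change and functional connectivity". On further terms: "Treatment seeking status (Treatment seeking vs non-treatment seeking) will be included as a between-subjects factor in these models". Nothing else enters this model. The deprivation ANCOVAs in the same section carry "nicotine dose as the covariate", but the genotype paragraph names no covariate.

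Section 12.1 states that "Efforts will be made to include ethnic minorities in proportion to their presence in the major metropolitan Baltimore area". Its target table for treatment seekers has the row "Black or African American 39 38 77" (females, males, total) out of 120. The corresponding row for non-treatment seekers gives 26 of 42. White participants are 39 and 15. Section 4.6 says that genotyping is carried out under a separate protocol, 10-DA-N457.

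**The concern.** The crossover randomises the order of the two patch conditions, so it protects the deprivation contrast. It does not protect a comparison of that contrast between genotype groups, because nobody is assigned a genotype. In a sample drawn mainly from two ancestry groups, short-allele carriers and the rest may differ in ancestry and in whatever goes with it. If one of those things alters the response to deprivation, the model has nowhere to put that difference except the genotype by deprivation term.

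The error can go either way. If the group with higher carriage responds more strongly to deprivation, Hypothesis 2.3 gains false support. If it responds less strongly, a true genotype effect is hidden. Section 11.3 tests a priori regions at 0.05, so an inflated error rate would pass straight into a reported finding.

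The protocol already treats race as worth balancing in another between-group imaging comparison: Sections 24.4 and 24.6 match the tDCS non-smokers on race, along with age, gender and education. Genotype groups cannot be matched in that way at recruitment, so the analysis is the place to deal with it.

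**Working it through.** **The plan's own figure.** Section 11.4 gives 16 to 35 participants for this interaction (d = 0.80 to 0.50, repeated-measures correlation 0.5, 80% power). Take f = d/2, two groups, two measurements, noncentrality λ = f²·N·2/(1 − 0.5), and 1 and N − 2 degrees of freedom.
- d = 0.50, N = 35: λ = 0.0625 × 35 × 4 = 8.75, power 81.9%. N = 34 already gives 80.7%.
- d = 0.80, N = 16: λ = 0.16 × 16 × 4 = 10.24, power 84.5%.

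The stated range reproduces. It assumes no confounding.

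**Planned race mix (Section 12.1).**
- Treatment seekers: 77/120 = 64.2% Black, 39/120 = 32.5% White.
- Non-treatment seekers: 26/42 = 61.9% Black, 15/42 = 35.7% White.
- Combined: 103/162 = 63.6% Black, 54/162 = 33.3% White, 5/162 = 3.1% Asian.

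The mix is nearly the same in both strata, so having treatment-seeking status in the model does little to adjust for ancestry.

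**Which differences can bias the interaction.** The interaction compares the within-person change (deprived minus non-deprived) between genotype groups. An ancestry difference in outcome level is present in both sessions and cancels. It would bias only the genotype main effect. What remains is an ancestry difference D in the change itself:

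bias = D × [Black share among the short-allele group − Black share among the long-allele group].

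If carriage is equal in the two ancestry groups, the bracket is zero.

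**Illustration.** None of these inputs is in the documents except the race mix and N: D in SD units of the change; carriage in Black and White participants of 0.50/0.50, 0.50/0.60, 0.45/0.65, 0.40/0.70 and 0.30/0.70; Black and White participants only, at 103:54 (65.6% and 34.4%); N = 85 + 35 = 120 completers; no true genotype effect; two-sided 5%.

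Worked case, 0.45/0.65 with D = 0.5:
- Short-allele share: 0.656 × 0.45 + 0.344 × 0.65 = 0.519, so groups of 62.3 and 57.7.
- Black share: 0.295/0.519 = 0.569 in the short-allele group and 0.361/0.481 = 0.750 in the long-allele group. The gap is 0.181.
- Size of bias: 0.181 × 0.5 = 0.09 SD.
- Variance of the change, including the ancestry mixture: 1 + 0.25 × 0.656 × 0.344 = 1.056.
- Standard error: √[1.056 × (1/62.3 + 1/57.7)] = 0.188. Noncentrality 0.0904/0.188 = 0.48.
- Rejection rate from the noncentral t on 118 degrees of freedom: 7.6%.

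| Carriage gap | Fraction of D carried over | Type I error, D = 0.2 | D = 0.3 | D = 0.5 (bias) |
|---|---|---|---|---|
| 0 points | 0 | 5.0% | 5.0% | 5.0% (0) |
| 10 | 0.09 | 5.1% | 5.2% | 5.7% (0.05 SD) |
| 20 | 0.18 | 5.4% | 6.0% | 7.6% (0.09 SD) |
| 30 | 0.27 | 6.0% | 7.2% | 11.0% (0.14 SD) |
| 40 | 0.37 | 6.8% | 9.0% | 16.1% (0.18 SD) |

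The last cell is 16.7% if the variance is taken as 1 without the mixture term. It also shifts slightly with the carriage levels chosen for a given gap.

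**The case against.** The strongest reply is that both links in the chain are assumed. The documents report no 5-HTTLPR frequency by ancestry and no ancestry difference in the response to deprivation. The larger figures need D = 0.5 SD, which equals the whole deprivation effect that Section 11.4 plans for (d = 0.5), together with a carriage gap of 30 to 40 points. At 0.2 to 0.3 SD most of the table is close to nominal. At N = 35, the upper size planned for this test, even D = 0.5 gives only 5.2 to 8.0%. This stands, and it limits the size of the concern.

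Three more points have some force. Section 11.2 describes itself as a summary, so its silence on a covariate is weaker evidence than silence in a full analysis plan. Ancestry data may exist under 10-DA-N457, which is not available here. And no primary outcome or sample-size driver rests on this hypothesis.

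A reader might also infer more than the documents support: that the genotype comparison is wholly unadjusted, or that any ancestry difference in the outcome would be credited to genotype. Neither follows. Treatment-seeking status is in the model, level differences cancel in the interaction, and in the table at most 37% of an ancestry difference in response carries over.

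What the reply does not supply is any handling of ancestry in this model. The within-person design does not provide it.

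**Conclusion.** The point holds as a conditional one. The model that tests Hypothesis 2.3 compares observed genotype groups in a mixed-ancestry sample without a race or ancestry term, and the interaction is confounded if carriage and deprivation response both differ by ancestry. Under the stated assumptions at N = 120, the error rate is about 5 to 9% for a response difference of 0.2 to 0.3 SD and about 6 to 17% for 0.5 SD. It stays at 5% if either difference is absent. Masking of a true effect is equally possible.

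These figures rest on assumed carriage and response differences, on enrolment targets rather than the race mix of completers, and on a two-group simplification. The point affects a secondary goal. It is worth acting on because the omission is clear and the remedy is cheap.

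**What to change.** In Section 11.2, add self-reported race/ethnicity **and its interaction with deprivation** to the 5-HTTLPR models. The interaction term does the work: a race main effect alone leaves the bias in the genotype by deprivation term untouched. State in advance how small categories are pooled, since only 5 Asian participants are planned. If ancestry components exist under 10-DA-N457, use those instead. Report the genotype split within each race/ethnicity group, so that readers can see whether carriage differs at all. Fixing the model now also removes a later choice between adjusted and unadjusted results.

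That race is recorded for each participant is an inference from the enrolment-by-race tables and the monitoring for skewed recruitment in Section 12.1. The main-protocol screening list in Section 4.3 does not name it, so this should be confirmed.

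The cost is wording, a few degrees of freedom and some precision where genotype and ancestry are correlated. At the 40-point gap the squared correlation is 0.367 × 0.40 = 0.147, so the variance of the genotype contrast rises by 1/(1 − 0.147) = 1.17 and its standard error by about 8%. At smaller gaps the loss is less. No visits or recruitment change.
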